## Study Summary

Title	Phase I/II, Open-Label Study to Determine Safety of Trifluoperazine (TFP) in Adults with Red Blood Cell Transfusion-Dependent Diamond Blackfan Anemia
Short Title	TFP in DBA
Protocol Number	17-0748
Phase	Phase I/II
Methodology	Open-Label, Non-Randomized
Study Duration	18-24 months
Study Center(s)	Single-center/Additional centers may be recruited if enrollment is slow
Objectives	To determine the safety and maximum tolerated dose (MTD) of TFP in red blood cell transfusion-dependent adults with Diamond Blackfan anemia
Number of Subjects	minimum 3, maximum 24
Diagnosis and Main Inclusion Criteria	Transfusion Dependent Adults Diagnosed with Diamond Blackfan Anemia
Study Product, Dose, Route, Regimen	Trifluoperazine (TFP) 1mg, 2mg, 5mg, or 10mg once daily by mouth
Duration of administration	Maximum of 21 days
Reference therapy	Red Cell Transfusion
Statistical Methodology	N/A- dose escalation study for safety/tolerability

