This class of drugs has not been tested specifically in subjects with DBA prior to this study. To mitigate the potential risks of administering TFP to this new population, we will (1) start dosing at dose levels well below those prescribed for psychosis over the past several decades, (2) dose escalate to a maximum of 10 mg daily (the lowest dose typically prescribed for psychosis), and (3) perform weekly safety monitoring. Given the positive signal in DBA animal models and the 60-year clinical experience with higher doses of TFP, this drug warrants a trial in humans to assess tolerability in DBA. If tolerated, this trial will support either a PoC trial of low-dose TFP in DBA, or the advancement of a chemically modified TFP-like drug (to alleviate the neurologic toxicity) for the treatment of DBA.

This is a dose escalation safety and tolerability study to evaluate the presence of TFP-related adverse events in DBA subjects, and to determine the maximum tolerated dose (MTD) of TFP in DBA. The dose escalation strategy is described in [Section 3.5 Dose Rationale and Risk/Benefits](#).

Some first-in-human (FIH) trials may implement an enrollment restriction rule such that two subjects are dosed in a given cohort, and a third subject is not dosed until both of the first two subjects have demonstrated tolerability. For this trial, we have elected not to use such an enrollment restriction design for the following reasons:

- a. This is not a FIH trial: TFP has been in wide clinical use for 60 years.
- b. Our dose levels (1 mg daily, up to max 10 mg daily) are all well within and below the safe range of clinical use. Doses in the 2-6 mg daily range have been shown to have a side effect profile similar to placebo in patients with anxiety ([Mendels, 1986](#)). A randomized clinical trial comparing TFP 15 mg/day vs. placebo in schizophrenic subjects revealed no difference in the rates of severe adverse effects, Parkinsonism or dystonia compared to placebo (Koch, 2014). Doses for psychosis range from 10 mg daily up to 40-50 mg daily, whereas we will dose at 1, 2, 5, and 10 mg daily only.

- c. We will monitor for safety, specifically for any hematologic toxicity and for extrapyramidal/central nervous system (CNS) effects. Dose escalation criteria and actions, as well as subject and cohort stopping rules are detailed in [Section 6 Study Design](#).

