### **3.5 Dose Rationale and Risk/Benefits**

In an *in vivo* mouse model of DBA, TFP at a dose of 5 mg/kg intraperitoneally every other day reduced apparent p53 activity and raised the RBC count and Hb level after 2 weeks of treatment (Macari, 2016). The murine dose scales allometrically to a daily dose of 12–15 mg of TFP in humans. As the 5 mg/kg dose was the only dose tested in the mouse study, and daily administration of TFP may be more efficacious than every other day dosing, it is possible that a daily dose of 5 mg or less in humans may be efficacious. Given the potential margin of error in the allometric calculation, a maximum dose of 10 mg daily may be tested in this trial.

The starting dose of TFP in subjects with DBA (1 mg) is lower than the starting dose in psychiatric indications, and the maximum TFP dose to be administered to subjects with DBA will not exceed 10 mg. As side effects of TFP have been shown to be dose-/plasma level-related, it is anticipated that the more severe side effects associated with TFP, including extrapyramidal symptoms, will be less likely to occur at doses  $\leq 10$  mg. The two trials cited in section [3.4 Clinical Data to Date](#) also support the likely tolerability of the proposed dose range in this trial ([Mendels, 1986](#); [Koch, 2014](#)).

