## 6 Study Design

### 6.1 General Design

This study is a multi-center, Phase I/II, dose escalation, open-label study to determine the safety of TFP in adult subjects with DBA and RBC-transfusion-dependence. A 3+3 dose escalation regimen will be used. The maximum time on study drug will be 21 days with a 1 week post-treatment follow-up period. It is expected that up to 24 subjects can be recruited and complete the study within 12-18 months. The dose escalation study design is shown in Figure 1:

- If 2 or more of the 6 subjects in Cohort B demonstrate toxicity  $\geq$  Grade 3, the study will be stopped, and 1 mg/day will be declared the MTD.
  - If  $< 2$  of the 6 subjects in Cohort B demonstrate toxicity  $\geq$  Grade 3 within 21 days of starting therapy, Cohort C will start.
3. Cohort C: Three subjects will receive TFP 5 mg PO daily.
- If there is no toxicity  $\geq$  Grade 3 at the end of the 21 days, Cohort D will start.
  - If 1/3 subjects in Cohort C demonstrates toxicity  $\geq$  Grade 3, an additional 3 subjects will be enrolled in Cohort C:
    - If 2 or more of the 6 subjects in Cohort C demonstrate toxicity  $\geq$  Grade 3, the study will be stopped, and 2 mg/day will be declared the MTD.
    - If  $< 2$  of the 6 subjects in Cohort C demonstrate toxicity  $\geq$  Grade 3 within 21 days of starting therapy, cohort D will start.
4. Cohort D: Three subjects will receive TFP 10 mg PO daily.
- If 0/3 subjects in Cohort D demonstrates toxicity  $\geq$  Grade 3, the study will be stopped, and 10 mg/day will be declared the MTD.
  - If 1/3 subjects in Cohort D demonstrates toxicity  $\geq$  Grade 3, an additional 3 subjects will be enrolled in Cohort D.
  - If 2 or more of the 6 subjects in Cohort D demonstrate toxicity  $\geq$  Grade 3, the study will be stopped, and 5 mg/day will be declared the MTD.
  - If  $< 2$  of the 6 subjects in Cohort D demonstrate toxicity  $\geq$  Grade 3 within 21 days of starting therapy, 10mg/day will be declared the MTD.

Each subject will undergo safety assessments as per the required schedule while on the study drug. All dosed subjects will be followed for an additional 1 week after discontinuing study drug (post-study safety follow-up). There will be no more than 6 subjects enrolled at any particular time.

Treatment will be discontinued for any subject if their Hb is > 12 gm/dL, not associated with RBC transfusions.

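### Section 6.1 declares 10 mg/day the MTD when Cohort D clears, although 10 mg is a preset ceiling and no dose has met the 6.1 failure rule

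*Combined protocol and SAP*

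**What the plan says.** **The aim.** The Study Summary gives the objective as "To determine the safety and maximum tolerated dose (MTD) of TFP in red blood cell transfusion-dependent adults", and Section 2 says the study is "to determine the maximum tolerated dose (MTD) of TFP in DBA". Section 4 is narrower and names only the safety profile at doses up to 10 mg/day.

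**The ceiling.** Section 3.5.1 lists four levels: 1, 2, 5 and 10 mg/day. Section 2 plans to "dose escalate to a maximum of 10 mg daily". Section 3.5 says "the maximum TFP dose to be administered to subjects with DBA will not exceed 10 mg" and explains the choice: "Given the potential margin of error in the allometric calculation, a maximum dose of 10 mg daily may be tested in this trial".

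**The decision rule.** In Section 6.1, 2 or more of 6 subjects with Grade 3 or higher toxicity in Cohort B, C or D stops the study and makes the next lower dose the MTD. Cohort D has two clearing branches. After 0/3, "the study will be stopped, and 10 mg/day will be declared the MTD". After fewer than 2/6, the text makes the same declaration.

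**A second rule.** Section 15.4, Scenario 2, rule (e) stops the study and declares 5 mg/day the MTD if 2 or more Cohort D subjects have one of the listed events. These include extrapyramidal symptoms, for which no explicit grade is set.

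**The concern.** Where Section 6.1 names 1, 2 or 5 mg/day as the MTD, the next dose up has failed, so the trial has found a limit between two tested doses. In the two Cohort D clearing branches nothing above 10 mg has been given. The trial stops there because the dose list ends, not because toxicity was seen. The same term then covers two different findings: a limit that was located, and a design that ran out of doses.

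This affects the outcome that the protocol leans towards. Of doses up to 10 mg, Section 3.5 says "it is anticipated that the more severe side effects associated with TFP, including extrapyramidal symptoms, will be less likely to occur". If that proves right, a team following the plan exactly would report its own design ceiling as a determined MTD, possibly on three subjects at that dose. What is at stake is the stated conclusion and how later readers use it.

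**Working it through.** **1. Reading of the design, checked against the plan's own figure.** Section 14.1 gives a minimum of 3 and a maximum of 24 subjects. Four cohorts of at most 6 give 4 × 6 = 24. A Cohort A that fails in its first three subjects gives 3. Both figures reproduce.

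**2. What each Section 6.1 outcome shows.**

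| Outcome under 6.1 | Dose named as MTD | Higher dose that failed |
|---|---|---|
| Cohort B fails | 1 mg/day | 2 mg/day |
| Cohort C fails | 2 mg/day | 5 mg/day |
| Cohort D fails | 5 mg/day | 10 mg/day |
| Cohort D clears, 0/3 | 10 mg/day | none tested |
| Cohort D clears, fewer than 2/6 | 10 mg/day | none tested |

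**3. Every path to a cleared Cohort D.** Each of the four cohorts must clear, either as 0/3 or as 1/6, so there are 2 × 2 × 2 × 2 = 16 paths, filling 12 to 24 cohort places. By construction none of the 16 contains a cohort that met the 6.1 failure rule.

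**4. What the Cohort D data say about 10 mg.** Exact (Clopper-Pearson) two-sided 95% intervals for the rate of Grade 3 or higher toxicity:
- 0/3: lower limit 0; upper limit 1 − 0.025^(1/3) = 0.708. Interval 0 to 70.8%.
- 1/6: lower limit 1 − 0.975^(1/6) = 0.004; the upper limit solves (1−p)^6 + 6p(1−p)^5 = 0.025, giving p = 0.641. Interval 0.4% to 64.1%.

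These are approximate here, because cohort size depends on the first three outcomes and Section 7.2, criterion 6, lets subjects re-enter from an earlier cohort.

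**5. How often the label would appear (illustration only).** The documents give no toxicity rates in DBA, so these are assumed: Grade 3 or higher rates of 1, 2, 3 and 5% at 1, 2, 5 and 10 mg. Only the 6.1 rule is applied. P(a cohort clears) = (1−p)^3 + 3p(1−p)^5.
- 1 mg: 0.9703 + 0.0285 = 0.9988
- 2 mg: 0.9412 + 0.0542 = 0.9954
- 5 mg: 0.9127 + 0.0773 = 0.9900
- 10 mg: 0.8574 + 0.1161 = 0.9734

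The product is 0.958. Cohort D opens with probability 0.984, so 0.984 × 0.8574 = 84.4% of trials reach the label through 0/3 and 0.984 × 0.1161 = 11.4% through 1/6.

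The answer moves with the assumption: 99.5% if the rate is 1% at every dose, 89.8% at 5%, 67.4% at 10%, and 30.9% for rates of 5, 10, 20 and 30%.

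Further assumptions: 2/3 or 3/3 stops the study, Cohorts A and B follow the Cohort C rule, and subjects are independent.

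**6. Sections 6.1 and 15.4 side by side.** Suppose none of three Cohort D subjects has Grade 3 or higher toxicity, but two have extrapyramidal symptoms of a lower grade. Section 6.1 gives 10 mg/day. Section 15.4 rule (e), read as written without a grade for these symptoms, gives 5 mg/day.

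**The case against.** The strongest reply is that MTD is often used loosely for the highest studied dose that cleared. On that usage every visible branch is coherent: a failing dose gives the level below, and a cleared top dose gives the top level. This stands. A reader might infer that the branches contradict each other, and they do not. But the looser usage still leaves 10 mg/day unable to show that a limit was found.

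A reader might also infer that the protocol never defines MTD. The copy reviewed does not show Figure 1 or the 6.1 text for Cohort A and the start of Cohort B, so that cannot be claimed. The point does not need it, because nothing above 10 mg is tested under any definition.

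A third tempting reading is that no dose has failed any rule when Cohort D clears. That is too strong. It holds for the 6.1 rule only; Section 15.4 can be met in the same cohort.

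The reply also notes that the ceiling is stated openly in several places, that MTD appears in neither the endpoints (Sections 6.2 to 6.4) nor the analysis (Sections 14.2 and 14.3), and that Section 2 ties the next step to tolerability. All of this is correct and limits the severity. It does not remove the MTD aim from the Study Summary and Section 2.

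Finally, assuming low toxicity and finding that cohorts usually clear is close to circular. That is fair, so the percentage is only an illustration. Nor can it be refined into a firm range by adding Section 15.4: that needs extrapyramidal rates and their overlap with Grade 3 or higher events, and the documents give neither.

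**Conclusion.** The point holds as one of labelling. When Cohort D clears under Section 6.1, the plan reports a ceiling fixed in advance as a determined MTD. The data support less: 10 mg/day was the highest dose tested and met the 6.1 tolerability rule, with an upper 95% limit for Grade 3 or higher toxicity of 70.8% after 0/3 or 64.1% after 1/6. This conclusion follows from the text and needs no assumed rate; the 95.8% illustration does.

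Severity is minor. No subject's treatment changes, and a careful reader can find the ceiling elsewhere in the protocol. The documents do not support going further and saying that 10 mg is poorly tolerated or that the escalation scheme is faulty.

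**What to change.** 1. In Section 6.1, for the two Cohort D clearing branches and only when no Section 15.4 stopping rule has been met in Cohort D, replace "10 mg/day will be declared the MTD" (and the same declaration in the fewer-than-2/6 branch) with: *MTD not reached; 10 mg/day is the highest dose tested and met the 6.1 tolerability rule.*
2. Align the aim in the Study Summary and Section 2, for example: *MTD, if reached at doses up to 10 mg/day.*
3. Reconcile Sections 6.1 and 15.4 for a Cohort D that clears the former but meets rule (e) of the latter. Which rule should govern is for the sponsor to settle.
4. Optionally, report beside the label the number of dosed Cohort D subjects with Grade 3 or higher toxicity and the exact 95% interval, marked as approximate.

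The cost is a few wording changes and one optional line in the report. No subjects or visits are added, and no dose, escalation step or stopping rule is proposed. The downside is a more modest conclusion when all cohorts clear.

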#### **3.5.1 Dose Escalation**

Up to 4 cohort dose levels of TFP will be studied: 1, 2, 5, and 10 mg/day for up to 21 days each, as tolerated. Cohort A will start at 1 mg/day, and the dose will escalate to 2 mg/day in Cohort B, 5 mg/day in Cohort C, and 10 mg/day in Cohort D. At the start of each cohort, 3 subjects will be enrolled, and an interim analysis (IA) for safety and tolerability will be

conducted after all 3 subjects have completed 21 days of treatment (See [Section 6 Study Design](#) for details). The 21-day time frame is based on the t1/2 from the healthy volunteer 5 mg single dose TFP study ([Midha, 1983](#)), showing that TFP's elimination t1/2 is approximately 12-14 hours. Therefore, steady state is reached approximately 3 days after initiating therapy, and 21 days of therapy provides at least 18 days of exposure at steady state (the 1 and 2 mg doses likely have shorter t1/2 and so steady state will be reached even sooner in the first 2 cohorts).

Whereas some FIH trials may use an enrollment restriction rule such that only two subjects are dosed at a time, this trial will not use such an enrollment restriction design. Please see [Section 2 Brief Summary of Research](#) for the supporting rationale.

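### In 6.1 the escalate and 10 mg exits count Grade 3+ toxicity to 21 days but the paired stop exits give no window, so an expanded cohort with a late event can meet both

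*Combined protocol and SAP*

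**What the plan says.** Section 6.1 sets out a 3+3 escalation in which an expanded cohort of six leaves by one of two exits.

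- **Fewer than two of six with Grade 3+ toxicity.** All three visible cohorts carry a 21-day limit: Cohort B, "within 21 days of starting therapy, Cohort C will start"; Cohort C, "within 21 days of starting therapy, cohort D will start"; Cohort D, "within 21 days of starting therapy, 10mg/day will be declared the MTD".
- **Two or more of six with Grade 3+ toxicity.** No time limit is stated. In Cohort C, "the study will be stopped, and 2 mg/day will be declared the MTD"; in Cohort D, "the study will be stopped, and 5 mg/day will be declared the MTD"; Cohort B is worded the same way and returns 1 mg/day.

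For the first three subjects of Cohort C, the escalate exit applies if there is no such toxicity "at the end of the 21 days, Cohort D will start", while the exit that adds three subjects after one of three is affected has no window. In Cohort D neither three-subject exit has a window, so those two do not conflict.

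The same section has subjects "followed for an additional 1 week after discontinuing study drug". Section 15.1 records adverse events to 7 days after the last dose, and section 9.5 has subjects questioned about them at Visit 4 (Day 29 ± 2). Section 3.5.1 places the interim safety look for the first three subjects of a cohort: it is "conducted after all 3 subjects have completed 21 days of treatment".

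**The concern.** A 3+3 rule gives one answer only if its two six-subject exits are complements. Here one exit counts to 21 days and the other has no end, while events are still being collected for a further week. A late event can therefore satisfy both.

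The MTD is a named objective in the Study Summary and in section 2. In an open-label trial of at most six subjects per dose, one late event can decide it. If both exits are met, someone must choose between two doses, or between escalating and stopping, after seeing the event. The choice should be fixed beforehand.

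A strict Day 21 cut is also awkward. The end-of-treatment examination and blood draw (Visit 3) is Day 22 ± 2, so a Grade 3 laboratory abnormality first found there may fall outside the count.

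**Working it through.** **1. Plan's own figure.** Section 14.1 gives 3 to 24 subjects. One cohort of three is 3; four cohorts of six is 4 × 6 = 24. This reproduces and is not in dispute.

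**2. The exits side by side.** Let E be the number of the six with a first Grade 3+ event by Day 21, and L the number with a first event after Day 21 but within the recording period.

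| Six-subject exit | Condition as written | Cohort B | Cohort C | Cohort D |
|---|---|---|---|---|
| Fewer than 2 | E < 2 | open C | open D | MTD 10 mg |
| 2 or more | E + L ≥ 2 | stop, MTD 1 mg | stop, MTD 2 mg | stop, MTD 5 mg |

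Both hold whenever E < 2 and E + L ≥ 2. The simplest case is E = 1, L = 1. No outcome meets neither exit. With the same count in both rows the conditions are complements and the overlap disappears: E = 1, L = 1 gives 10 mg under a common 21-day window and 5 mg under a common Day 29 window.

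The conflict is clear from Day 23. Day 22 is arguable, since 21 days after a Day 1 start is Day 22.

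**3. How often.** The documents give no event rates, so these are assumptions:
- p = chance that a subject has a first Grade 3+ event by Day 29: 0.05, 0.10 or 0.25.
- g = share of those first events that fall after Day 21: 8/29 (uniform onset over 29 days), range 10% to 50%.
- q = p(1 − g) = chance of a first event by Day 21.
- Subjects are independent, expansion is decided on the Day 21 count as 3.5.1 suggests, and no 15.4 stop has intervened.

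Expansion needs exactly one of the first three affected by Day 21. The conflict then needs none of the other five affected by Day 21 and at least one of them affected later:

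P(both exits) = 3q[(1 − q)^5 − (1 − p)^5]

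With g = 8/29:
- p = 0.05: q = 0.0362; 0.1086 × (0.8316 − 0.7738) = 0.0063
- p = 0.10: q = 0.0724; 0.2172 × (0.6867 − 0.5905) = 0.0209
- p = 0.25: q = 0.1810; 0.5431 × (0.3684 − 0.2373) = 0.0712

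With g = 0.10:
- p = 0.05: 0.135 × (0.7944 − 0.7738) = 0.0028
- p = 0.10: 0.270 × (0.6240 − 0.5905) = 0.0091
- p = 0.25: 0.675 × (0.2796 − 0.2373) = 0.0285

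With g = 0.50:
- p = 0.05: 0.075 × (0.8811 − 0.7738) = 0.0080
- p = 0.10: 0.150 × (0.77378 − 0.59049) = 0.02749
- p = 0.25: 0.375 × (0.5129 − 0.2373) = 0.1034

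These are chances once Cohort D opens. The same formula gives escalate-and-stop in B or C at the same p. Among cohorts that expand, divide by 3q(1 − q)². At p = 0.10 and g = 8/29 that is 0.0209 / (0.2172 × 0.9276²) = 0.112.

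**4. Does another section decide?** Section 15.4 Scenario 2 also has no window. It covers the named neurological syndromes, and otherwise repeated serious or Grade 3+ events judged related to TFP; 6.1 counts any Grade 3+ toxicity. It states no precedence over 6.1. Where it applies in Cohort D it returns 5 mg, but the 10 mg exit in 6.1 remains met.

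**The case against.** The strongest reply is that the two bullets are halves of one count, so the 21 days in one half governs both. Much supports this. Section 3.5.1 justifies the 21-day time frame and refers to section 6 for details; Cohort C speaks of the end of the 21 days; the primary objective in section 4 is the safety of a 21-day course; and 6.1 describes the extra week as follow-up after the study. That stands as evidence of intent. It does not supply the missing words: 3.5.1 times the look for the first three subjects only, and nothing visible says that later events are excluded from the stop count.

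Second, Figure 1, Cohort A and the start of Cohort B are absent from the extracted text, and a general window could be stated there. That also stands, so the point is limited to the visible exits.

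Third, late first events may be uncommon: section 3.2.2 gives a mean half-life of 12.5 hours, and section 10 says dystonia may occur in the first days of treatment. This argues for the lower end of the range for g.

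Fourth, the MTD is not in the section 4 objective or the 6.2 endpoints, and section 14.2 summarises all adverse events. No safety data are lost; what is affected is the dose decision.

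**Conclusion.** The point holds as a conflict between decision rules. As the visible text stands, an expanded Cohort D with one subject affected by Day 21 and a second afterwards yields both 10 mg and 5 mg as the MTD; the same pattern in B or C both escalates and stops. This follows from the wording and needs no assumed rate.

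Its expected frequency is modest: about 0.6% at p = 0.05 (0.3% to 0.8% as g runs from 10% to 50%), 2.1% at p = 0.10 (0.9% to 2.7%) and 7.1% at p = 0.25 (2.9% to 10.3%). Both p and g are assumptions.

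Two stronger readings are not supported. A reader might infer that the trial has no toxicity window at all; the documents point to 21 days as the probable intent and merely fail to write it into the stop exits. A reader might also let expansion depend on events to Day 29, which raises the figures to about 1%, 3% and 10%; section 3.5.1 places that look after 21 days of treatment, so the smaller figures are the better guide.

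It should be fixed because the contradiction touches a named objective and is cheap to remove.

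**What to change.** Put the same window in every expand, escalate, stop and MTD exit of every cohort in 6.1.

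- **Minimum:** add the existing 21-day limit to each exit that lacks it.
- **Preferred:** count Grade 3+ toxicity from first dose through the later of Day 21 and the Visit 3 assessment, and hold the dose decision, including the 3.5.1 interim look, until the last subject's Visit 3. Taking the later of the two matters because Visit 3 may fall as early as Day 20, before dosing ends. It also brings end-of-treatment laboratory results into the count.
- **Precedence:** add one sentence that where 15.4 Scenario 2 is met, it overrides an escalate or 10 mg exit in 6.1.
- **Check:** read Cohort A, the start of Cohort B and Figure 1 for the same wording.

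A separate recount of events after the window is not needed; it would reintroduce a second window.

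The cost is text only, with no added visits, data or subjects. The preferred window adds at most 24 − 21 = 3 days per dose decision: 4 × 3 = 12 days over four unexpanded cohorts, or 8 × 3 = 24 if all four expand. For a subject whose last dose is Day 21, it closes before the earliest re-entry allowed by 7.2 (21 + 6 = Day 27).
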